Exclusion Criteria	Type 1 diabetes Serum glucose < 80mg/dl at enrollment Systolic blood pressure < 90mmHg at enrollment Requirement of intravenous inotropic therapy at enrollment or anticipated need of therapy during the study period History of hypersensitivity to any SGLT2 inhibitors Women who are pregnant or breastfeeding Severe anemia (Hemoglobin < 7.5g/dl) Severe uncorrected aortic or mitral stenosis Inability to perform standing weights or measure urine output accurately History of diabetic ketoacidosis Chronic combination nephron blockade with loop and thiazide therapy as an outpatient scheduled daily for more than 7 days prior to admission (Does not include HCTZ < 50mg for blood pressure) Diffuse anasarca with 4+ edema and projected hypervolemia exceeding 40-pounds Severe hepatic impairment (Child-Pugh class C if severity of hepatic failure is in question) Clinical picture consistent with acute myocardial infarction including troponin elevation or ischemic changes on electrocardiogram Site investigator determines the subject is not a good candidate to participate in study at this time

Primary Endpoint	cumulative change in weight (kilograms) per 40mg of IV furosemide equivalents from enrollment to day 5 or discharge (if earlier) between protocolized diuretic therapy and dapagliflozin plus protocolized diuretic therapy guided by urine output			
Assessment Schedule (Appendix A)	Baseline : standing weight, NT-proBNP, BMP, hemoglobin A1c, spot urine values of sodium, potassium, and creatinine (calculate urine sodium/potassium ratio, FENa), vital signs, study loop diuretic and diabetic medication orders, congestion score, document baseline HF and diabetic medications, start urine output quantification, urine biobanking for future investigations including urinary exosomes.			
	Daily: standing weight, BMP, vital signs, urine output quantification, titration of study loop diuretic and diabetic medication orders, document HF and diabetic medications, adverse event assessment			
	Day 2 : daily assessments as above plus 2-hour post loop diuretic spot urine sodium, potassium, and creatinine. Calculate FENa, 6-hr sodium output, urine sodium/potassium ratio, 24-hour urine collection for quantification and diuretic efficiency calculation, urine biobanking for future investigations including urinary exosomes.			

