 - ii. Mild: serum glucose 54-69 mg/dl
 - iii. Mod-Severe: serum glucose < 54 mg/dl
 - b. Hyperglycemia is defined as:
 - a. Not hyperglycemic: serum glucose < 200 mg/dl
 - b. Mild: serum glucose 200-300 mg/dl
 - c. Severe: serum glucose > 300 mg/dl
- d) Incidence of hypovolemic hypotension, defined as symptomatic hypotension with a sustained systolic blood pressure less than 90 mmHg lasting at least 30 minutes requiring fluid administration.
- e) Inpatient mortality

Design Considerations

Randomization

Patients will be randomized in a 1:1 ratio to receive either intervention or structured usual care. Randomization will use block randomization stratified by site with block sizes of 4.

Power and Sample Size

We anticipate dapagliflozin will increase the weight loss while decreasing the cumulative furosemide dose required to achieve euvolemia. On the basis of the historical literature, we project an increase in diuretic efficiency by 0.1kg/40mg IV furosemide in the Dapagliflozin arm to be a clinically meaningful difference. We project that our diuretic protocol will decrease variations in loop diuretic dosing, which drive large standard deviations. We project a normally distributed standard deviation within each arm to be 0.25kg/40mg. A sample size of 120 experimental subjects and 120 control subjects will have 87% power to detect a probability of 0.611 that an observation in the Dapagliflozin arm is less than an observation in the structured usual care arm using a Wilcoxon (Mann-Whitney) rank-sum test with a 0.05 two-sided significance level.

Statistical Approach

Descriptive Analysis

Initially, we will describe the study cohort pooled across all sites, both overall and grouped by treatment assignment. To characterize the study sample, demographic, clinical, and lab data will be described overall and by treatment arm. Categorical variables will be described using frequencies and proportions; continuous variables will be described using means and standard deviations as well as medians and interquartile ranges (IQR). Missingness will be recorded for each variable. To further assess the distribution of variables, graphical summaries will be displayed using graphs such as box-plots, dot-plots,

violin-plots, and/or histograms. No statistical testing will be done to compare characteristics across groups. At a minimum, the following baseline variables will be described:

- Age (years)
- Sex

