- b) A time to event analysis is proposed to assess the association of 30-day hospital readmission for ADHF or diabetes-related reasons. Cumulative incidence of hospital readmission for heart failure or diabetes-related reasons will be graphed by treatment arm death as a competing risk. Multivariable Cox proportional hazards models stratified by enrollment site will be fit to assess the association of time to hospital readmission for reasons of interest with treatment assignment.

Exploratory Analyses:

Appropriate model diagnostics will be run to assess model fit. If model diagnostics suggest the planned approach violates necessary assumptions, alternative methods will be pursued.

- a) The association of NT-proBNP at discharge with treatment arm will be modeled using covariateadjusted PO regression, adjusting for NT-proBNP at baseline (Day 1).
- b) The association of Day 2 24-hour total urine output per the following methods in which diuretic dose is centered at 40mg and values less than 40mg are winsorized to 40mg:
 - a. 40 mg of IV furosemide equivalents will be analyzed using the Wilcoxon Rank Sum test
 - b. Doubling of the loop diuretic dose to account for the logarithmic dose-response curve will be analyzed using the Wilcoxon Rank Sum test.
- c) Urine sodium-based diuretic efficiency defined as the Day 2 24-hour total urine sodium excretion (mmol) per 40mg of IV furosemide equivalents (total loop diuretic dose over Day 2) will be analyzed using the Wilcoxon Rank Sum test.
 - a. Repeated as per doubling of the cumulative Day 2 loop diuretic dose (log2 cumulative loop diuretic dose centered at 40mg) will be analyzed using the Wilcoxon Rank Sum test.
- d) Spot urine sodium-based diuretic efficiency defined as the spot urine sodium concentration (mmol/L) on Day 2 per 40mg of IV furosemide equivalents (preceding loop diuretic dose) will be analyzed using the Wilcoxon Rank Sum test.
- e) The association of Day 2 fractional excretion of sodium (FENa)-based diuretic efficiency determined from spot urine collected 2 hours after bolus loop dose with treatment arm will be analyzed using the Wilcoxon Rank Sum test.
- f) The association of Day 2 urinary Na/K ratio with treatment arm will be analyzed using covariateadjusted PO regression, adjusting for baseline (Day 1) urinary Na/K ratio.
- g) The association of calculated Day 2 6-hour sodium output with treatment assignment will be analyzed using the Wilcoxon Rank Sum test

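### Day 2 spot sodium efficiency, FENa efficiency and 6-hour sodium output are compared without the baseline spot urine already collected; adjusting for it would match the Na/K analysis and could add precision

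*SAP*

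**What the plan says.** **Planned tests.** In SAP Exploratory Analyses, item g) reads "The association of calculated Day 2 6-hour sodium output with treatment assignment will be analyzed using the Wilcoxon Rank Sum test". Items d), spot sodium per 40 mg, and e), FENa per 40 mg, use the same test, also without a covariate. Item f), the Na/K ratio, uses PO regression "adjusting for baseline (Day 1) urinary Na/K ratio".

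**Data collected.** The Assessment Schedule in the protocol's Clinical Trial Summary lists at baseline "spot urine values of sodium, potassium, and creatinine (calculate urine sodium/potassium ratio, FENa", and the same three analytes on Day 2. Appendix A marks spot urine electrolytes at baseline and Day 2 only, each about 2 hours after an IV loop dose. FENa, 6-hour sodium output and the Na/K ratio are all calculated from the Day 2 sample.

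**Supporting text.** Protocol section 10.0 notes that the Wilcoxon test is contained in the PO model and that the PO model can also adjust for baseline. The SAP's Main Analysis plans multiple imputation for missing covariates. Its heterogeneity list already includes Day 1 FENa-based efficiency per 40 mg.

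**Not stated.** The SAP gives no reason for leaving d), e) and g) unadjusted. Neither document gives a power figure for these endpoints or a correlation between baseline and Day 2 values.

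**The concern.** Patients differ in how much sodium they excrete after a loop dose. If those differences persist from baseline to Day 2, an unadjusted comparison leaves them in the error term, although the data to remove part of them are on file.

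There is also a consistency problem. Endpoints from one sample would be analysed in two ways, so a different result for the Na/K ratio and for FENa efficiency could reflect the method and not the physiology. These endpoints are part of the trial's evidence on natriuresis, alongside b) 24-hour urine output, c) 24-hour urine sodium and f) the Na/K ratio.

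**Working it through.** **1. The four endpoints side by side**

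| SAP item | Planned analysis | Baseline counterpart in the documents |
|---|---|---|
| d) spot sodium per 40 mg | Wilcoxon, no covariate | Baseline spot sodium is collected; a per-40 mg value also needs the preceding dose |
| e) FENa per 40 mg | Wilcoxon, no covariate | Day 1 FENa-based efficiency, already a heterogeneity variable |
| f) Na/K ratio | PO, baseline-adjusted | Baseline Na/K ratio |
| g) 6-hour sodium output | Wilcoxon, no covariate | None listed; the output is calculated on Day 2 only. Baseline spot sodium is available |

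Appendix A has no separate Day 1 spot urine and f) labels its baseline as Day 1, so the Day 1 FENa value should be the baseline sample.

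**2. The plan's own power figure, as a reference**

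The only power statement concerns the primary endpoint (SAP, Power and Sample Size): "A sample size of 120 experimental subjects and 120 control subjects will have 87% power to detect a probability of 0.611", "using a Wilcoxon (Mann-Whitney) rank-sum test with a 0.05 two-sided significance level". Its inputs are "we project an increase in diuretic efficiency by 0.1kg/40mg IV furosemide in the Dapagliflozin arm" and "We project a normally distributed standard deviation within each arm to be 0.25kg/40mg", with 1:1 allocation.

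- Standardised effect: 0.1 / 0.25 = 0.4.
- Implied probability: Φ(0.4/√2) = 0.611, as stated.
- Normal two-sample power: Φ(0.4/√(2/120) − 1.960) = Φ(3.098 − 1.960) = 0.8725, which reproduces 87%.
- With the Wilcoxon efficiency 3/π: Φ(3.098 × 0.977 − 1.960) = 0.857. A simulated Wilcoxon (20,000 runs) gives 0.852.
- Noether's formula with 0.611: Φ(√(12 × 240 × 0.25) × 0.111 − 1.960) = 0.846.

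The setting of effect 0.4 and 120 per arm is borrowed below for illustration only. It is not a projection for the spot-urine endpoints.

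**3. Effect of adjustment**

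With correlation r (an assumption), normal theory multiplies the residual variance by 1 − r², so the equivalent sample-size factor is 1/(1 − r²). As a check on the actual methods, 1,000 trials were simulated at each of five values of r with a normal outcome. Each trial was analysed by Wilcoxon and by PO regression on treatment and a linear baseline term.

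| r | 1 − r² | 1/(1 − r²) | Sample-size equivalent | Power, Wilcoxon | Power, adjusted PO |
|---|---|---|---|---|---|
| 0 | 1.00 | 1.00 | 0% | 0.854 | 0.854 |
| 0.2 | 0.96 | 1.04 | 4% | 0.862 | 0.885 |
| 0.3 | 0.91 | 1.10 | 10% | 0.840 | 0.880 |
| 0.5 | 0.75 | 1.33 | 33% | 0.868 | 0.957 |
| 0.6 | 0.64 | 1.56 | 56% | not simulated | not simulated |
| 0.7 | 0.51 | 1.96 | 96% | 0.858 | 0.988 |

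The Wilcoxon ignores the baseline, so its power does not depend on r. The spread from 0.840 to 0.868 is simulation error: the standard error is √(0.852 × 0.148/1000) = 0.011. Within the same simulated trials, adjustment changed power by 0, 2.3, 4.0, 8.9 and 13.0 points at r = 0, 0.2, 0.3, 0.5 and 0.7. The simulation assumed no missing baselines.

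**The case against.** The strongest reply is that nothing here is an error. The endpoints are exploratory and the unadjusted Wilcoxon is valid under 1:1 randomization. The SAP also follows the endpoint definitions, since among these four only the Na/K ratio is defined as baseline-adjusted. All of that stands.

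The size of the gain is also open to challenge, and that stands too:

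- **r may be low.** The baseline sample may follow an open-label dose given before randomization, while the Day 2 sample may follow titration. Items d) and e) also divide by doses that can differ between the two days.
- **1 − r² is a normal-theory factor**, not a property of PO regression. The simulation supports the direction and rough size, but with a borrowed effect size. The adjusted odds ratio is also a conditional estimand.
- **The baseline is not always an exact match.** Item g) has none listed, and for d) the schedule does not list the dose preceding the baseline sample.
- **Some baseline samples may be too late.** Appendix A says that baseline may be Day 1 and that the sample can, not must, precede randomization. Setting late samples to missing and imputing them would erode the gain by an unknown amount. The same weakness already affects f).

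These points limit the gain and shape the fix. They do not supply a reason to analyse endpoints from one sample in two ways, and at r = 0 the adjusted model lost no measurable power.

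**Conclusion.** The point holds as a low-priority improvement in precision and consistency. Items d), e) and g) can be adjusted with data already collected, by the model the SAP uses for f) and on the rationale the protocol itself gives. The gain ranges from nothing at r = 0 to the equivalent of 33% more patients at r = 0.5 and 56% at r = 0.6. It rests on an assumed r, on normal-theory variance and on mostly complete baselines.

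A reader might infer more than the documents support:

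- **Bias or an inflated type I error.** Neither follows, because the unadjusted test is valid.
- **A known loss of precision, recoverable at no cost.** The documents give no r, the loss may be close to zero, and late samples carry a cost.
- **An unanswered mechanism question.** Items b), c) and f) also bear on natriuresis, and c) measures 24-hour sodium excretion directly.
- **A departure of the SAP from the protocol.** The protocol attaches baseline adjustment to the Na/K ratio but not to FENa efficiency or 6-hour output. Spot sodium efficiency appears only in the SAP.

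**What to change.** Amend SAP Exploratory Analyses d), e) and g) to PO regression on treatment, each with a named baseline covariate:

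- **d)** baseline spot sodium, expressed per 40 mg if the preceding loop dose is recorded;
- **e)** Day 1 FENa-based efficiency per 40 mg, as in the heterogeneity list;
- **g)** baseline spot sodium, since no baseline 6-hour output or formula for one is given.

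A restricted cubic spline with 3 knots may be used, as for baseline weight in the primary model. Item f) does not specify a spline, so the form should be stated for all four.

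Add one timing rule that works the same way in both arms: only samples taken before randomization count as the covariate. A cut-off at the first dapagliflozin dose would be undefined in the control arm. Apply the rule to f) as well, and treat later samples as missing covariates under the multiple imputation already planned. Report how many are imputed in each arm. Keep the unadjusted Wilcoxon as a supportive result.

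**Cost.** Three analysis lines and one timing rule, with no new sampling. Sample times must be compared with randomization times. The gain will be smaller if many baselines are imputed or r is low.

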10.0 Statistical Methods

The full statistical methods are detailed separately in the Statistical Analysis Plan.

The primary analysis model will be the semiparametric proportional odds (PO) ordinal logistic regression model¹⁶ for continuous outcome variables¹⁷. The PO model does not make any distributional assumption for the response variable, is robust to extreme values, and is invariant to transformations of the response variable. It is also extremely efficient when compared to linear regression if normality holds. The Wilcoxon nonparametric two-sample test is a special case of the PO model, but the PO model allows for baseline covariate adjustment. Note that we use covariate adjustment instead of change from baseline so as to not assume that (1) the baseline variable is linearly related to the response variable and (2) the slope of the baseline variable is 1.0.

For binary outcomes we will use the special case of the PO model that is the binary logistic regression model.

For safety analysis of clinical lab variables we use the most powerful and least arbitrary continuous variable analyses and include the empirical cumulative distribution function of post-randomization values of these variables. These continuous analyses will also provide estimates of incidence of such outcomes as hyper- and hypo-kalemia, but will be more sensitive than using only binary responses.

Trial	Experimental agent	Mean decrease in weight (kg) Experimental, (%)	Mean decrease in weight Control, (%)	Within group SD in Experimental Group (kg)
TRUE-AHF ⁸	Ularitide			
RELAX-AHF ¹⁸	Serelaxin	3.6	3.0	4.4
ASCEND-HF ⁹	Nesirtide			
EVEREST ¹⁹	Tolvaptan	3.3	2.7	3.3
TACTICS ²⁰	Tolvaptan	3.7	2.5	4.4
Secrets of HF ²¹	Tolvaptan	3.5	2.4	2.0
ROSE-HF ²²	Nesiritide	3.25	3.5	0.9
ROSE-HF ²²	Dopamine	3.4	3.5	0.9
MEAN		3.5	2.9	2.7

Changes in body weight from admission to discharge in previous literature

Changes in weight by IV 40mg Furosemide Equivalents (FE)

Trial	Experimental agent	Duration (days)	Daily IV loop diuretic dose in FE, mean or median (IQR)*	Median (IQR) decrease in weight (kg)/40mg IV FE	Difference associated with adverse HF outcomes
RELAX-AHF ²³	Serelaxin	5	80	0.42 (1.00, 0.14)	Below median value
DIUR-HF ¹⁴	None	3-5	137 (100, 200)	0.20 (0.281, 0.082)	Below median value
ASCEND-HF ²⁴	Nesiritide	2		0.42 (1.0, 0.05)	Below median value
PROTECT ²⁵	Rolofylline	4	80 (47, 133)	0.38 (0.8, 0.13)	Below median value
EVEREST ^{19,26}	Tolvaptan	4	80	0.30 (0.79, 0.03)	Below median value

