 - a. Repeated as per doubling of the cumulative Day 2 loop diuretic dose (log2 cumulative loop diuretic dose centered at 40mg)
- d) Spot urine sodium-based diuretic efficiency defined as the spot urine sodium concentration (mmol/L) on Day 2 per 40mg of IV furosemide equivalents (preceding loop diuretic dose)
- e) Fractional excretion of sodium (FENa)-based diuretic efficiency on Day 2 of IV therapy defined as the FENa from a spot urine test on Day 2 of IV therapy collected ~2 hours after bolus loop dose per 40 mg of IV furosemide equivalents.
 - a. Repeat as per doubling of the cumulative loop diuretic dose (log2 cumulative loop diuretic dose centered at 40mg)
- f) Urinary Na/K ratio at Day 2 of IV therapy adjusted for baseline.
- g) Calculated 6-hour sodium output on Day 2 of IV therapy using spot urine sodium collected 2 hours after bolus loop dose.
- h) Length of hospital stay, measured as days from admission to discharge
- i) Presence of symptoms of congestion and dyspnea at discharge, measured via blinded-physician exam and patient reported congestion scores.
- j) Hospital readmission within 30 days of discharge for any cause.
- k) Number of days at home without hospitalization or emergency room visit during 30-day follow up period.
- 1) Mean serum glucose during therapy
- m) Amount of total daily insulin doses (units) utilized per day during therapy, compared between treatment arms and to a "prior to enrollment" outpatient insulin regimen.
- n) Analyze the change in basic metabolic panel laboratory values and hemoglobin from baseline to end of study
- o) Serum potassium covariate with attention to both elevation and depression.

Hypokalemia levels are defined as

- a. Not hypokalemic: serum potassium > 3.4 mEq/L
- b. Mild: serum potassium 3.0 3.4 mEq/L
- c. Mod-Severe: serum potassium < 3.0 mEq/L

Hyperkalemia levels are defined as

- a. Not hyperkalemic: serum potassium < 5.1 mEq/L
- b. Mild: serum potassium 5.1 5.5 mEq/L
- c. Severe: serum potassium > 5.5 mEq/L

Safety Endpoints: Comparing differences among the two arms in the following:

- a) Estimated Glomerular Filtration Rate by the MDRD equation at discharge adjusted for baseline. A sensitivity analysis of eGFR by the CKD-EPI equation will also be done.
- b) Incidence of ketoacidosis as adjudicated by the CEC
- c) Serum glucose with attention to both elevation and depression.
 - a. Hypoglycemia is defined as:
 - i. Not hypoglycemic: serum glucose > 70 mg/dl

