- h) The association of length of hospital stay with treatment assignment will be analyzed using the Wilcoxon Rank Sum test

- The association of presence of symptoms of congestion and dyspnea at discharge measured via blinded physician exam and patient reported congestion scores with treatment assignment will be analyzed using the Pearson chi-square test. A proportional odds model will be used to assess the association of discharge congestion score with treatment assignment, adjusting for baseline congestion.
- j) Cumulative incidence of all cause hospital readmission within 30 days of index hospitalization discharge will be graphed by treatment arm treating death as a competing risk. The association of all cause hospital readmission within 30 days of index hospitalization discharge with treatment assignment will be analyzed using the Pearson chi-square test.
- k) The association of number of days at home without hospitalization or emergency room visit during the 30-day follow-up period with treatment assignment will be analyzed using the Wilcoxon Rank Sum test. For purposes of analysis, subjects who died within 30 days of the index hospital discharge will be assigned a value of 0 days at home
- 1) The association of mean serum glucose during therapy with treatment assignment will be analyzed using the Wilcoxon Rank Sum test
- m) Total daily insulin doses (units) utilized per day during therapy will be compared between treatment arms in all comers and in those with diabetes at baseline using a Wilcoxon Rank Sum Test. Total daily insulin doses utilized per day during therapy will be compared to a 'prior to enrollment' utilization using the Wilcoxon Signed Rank Test.
- n) The change in basic metabolic panel laboratory values and hemoglobin from baseline to the end of study will be compared across treatment groups using the Wilcoxon Rank Sum test.
- o) Serum potassium trends over time by treatment assignment will be graphed. Descriptive statistics
 of the daily raw potassium values and kalemic status during hospitalization by treatment group
 will be reported and compared across treatment assignments by Wilcoxon Rank Sum tests and
 Pearson's chi-square tests, respectively.

Safety Analyses:

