All multivariable models will adjust for the same key covariates as specified for the primary outcome, as sample size permits. Appropriate model diagnostics will be run to assess model fit. If model diagnostics suggest the planned approach violates necessary assumptions, alternative methods will be pursued.

- a) The association of estimated Glomerular Filtration Rate (eGFR) at discharge, calculated using the MDRD equation, with treatment assignment will be modeled using covariate-adjusted PO regression, adjusting for baseline eGFR. The analysis will be repeated calculating eGFR using the CKD-EPI equation as well.
- b) The association of the incidence of ketoacidosis as adjudicated by the CEC with treatment assignment will be analyzed using the Pearson chi-square test.
- c) Serum glucose trends over time by treatment assignment will be graphed. Descriptive statistics of the daily raw glucose values and the glycemic status during hospitalization by treatment group will be reported and compared across treatment assignment by Wilcoxon Rank Sum tests and Pearson's chi-square tests, respectively.
- d) The association of incidence of hypovolemic hypotension, defined previously, with treatment assignment will be analyzed using the Pearson chi-square test.

e) The association of inpatient mortality with treatment assignment will be analyzed using the Pearson chi-square test and univariate logistic regression.

Sensitivity Analyses:

Our sensitivity analysis will be a covariate-adjusted proportional odds (PO) regression model with our outcome being log-transformed weight at the minimum of Day 5 or discharge and the main predictor being treatment assignment. Adjusting covariates will be as defined in the primary analysis. Appropriate model diagnostics will be run to assess model fit. If model diagnostics suggest the planned approach violates necessary assumptions, alternative methods will be pursued.

Heterogenicity of Treatment Effect:

Heterogenicity of Treatment Effect (HTE) will be assessed refitting the primary model with the covariate of interest interacted with treatment assignment. The HTE analysis will include the following variables:

- Sex (male or female)
- Baseline edema score (No-Mild/Moderate/Severe)
- Baseline NTproBNP
 - Continuous
 - Dichotomize by median NTproBNP [above/below]
- Baseline BMI-adjusted BNP: defined as a 4% increase in NT-proBNP for every 1 unit increase in baseline BMI above a BMI of 20kg/m²
 - Continuous

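### SAP exploratory n) tests laboratory change scores without baseline adjustment: a valid but less precise choice, left unexplained, that costs almost nothing to replace

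*SAP*

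**What the plan says.** The SAP's list of exploratory endpoints defines item n) as a change score: "Analyze the change in basic metabolic panel laboratory values and hemoglobin from baseline to end of study". Exploratory Analyses n) then gives the analysis: "The change in basic metabolic panel laboratory values and hemoglobin from baseline to the end of study will be compared across treatment groups", by the Wilcoxon rank sum test. No baseline covariate enters. The SAP's change log shows that the serum chemistry comparison was added in version 2.0, and the protocol's own list of exploratory outcomes (section 2.3) does not contain it.

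Protocol 10.0, in the paragraph that introduces the proportional odds (PO) model as the primary analysis model, says "we use covariate adjustment instead of change from baseline so as to not assume that (1) the baseline variable is linearly related" to the response and that "the slope of the baseline variable is 1.0". For safety laboratory data it adds: "For safety analysis of clinical lab variables we use the most powerful and least arbitrary continuous variable analyses".

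Elsewhere the SAP follows that reasoning. Exploratory a) (NT-proBNP), f) (urinary Na/K) and the PO model for the discharge congestion score all adjust for the baseline value. In Safety Analyses a), eGFR at discharge is "modeled using covariate-adjusted PO regression, adjusting for baseline eGFR".

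**The concern.** A change score fixes the baseline coefficient at 1. If the true slope is below 1, subtracting the whole baseline value adds noise that a fitted slope would not. This is the assumption that protocol 10.0 gives as its reason for preferring adjustment, and n) makes it without comment.

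Scale is a second issue. Protocol 10.0 favours the PO model partly because its result does not change when the response is transformed. A rank test on differences lacks that property. A patient with a high baseline can have the larger absolute change but the smaller proportional change, so ranks of raw changes and ranks of log changes can differ.

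What is at stake is precision in an exploratory comparison, and consistency between related results. Creatinine, a usual member of the panel, would be tested as an unadjusted change, while the eGFR computed from it is modelled with baseline as a covariate.

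**Working it through.** **The plan's own figure.** The documents give no power or precision figure for n). The only stated power, 87% with 120 per arm, is for the primary endpoint. It reproduces: Φ(0.1/(0.25√2)) = 0.611, and a two-sample normal calculation with difference 0.1, SD 0.25 and two-sided 0.05 gives 0.8725. It says nothing about n).

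**Inputs.** From the documents: 120 per arm, 1:1 allocation, a change score in n) with no covariate. Assumed: equal variance σ² at baseline and end of study, a linear relation between the two, and their correlation r. The documents state no r for any laboratory value, so a range is shown.

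**Formulas.**
- Variance of a change score: 2σ²(1 − r).
- Residual variance after adjustment for baseline: σ²(1 − r²).
- Ratio, adjusted to change: (1 − r²)/[2(1 − r)] = (1 + r)/2.
- Extra patients needed by the change score: 2/(1 + r) − 1.
- Extra width of its confidence interval: √[2/(1 + r)] − 1.
- Adjusted patients that 240 change scores are worth: 240(1 + r)/2.
- Power with adjustment where the change score has 80%: Φ(2.802·√[2/(1 + r)] − 1.960), with 2.802 = 1.960 + 0.842.

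| r (assumed) | Variance ratio | Extra patients | Wider CI | 240 worth | Adjusted power if change has 80% |
|---|---|---|---|---|---|
| 0.3 | 0.65 | 54% | 24.0% | 156 | 93.5% |
| 0.5 | 0.75 | 33% | 15.5% | 180 | 89.9% |
| 0.7 | 0.85 | 18% | 8.5% | 204 | 86.0% |
| 0.9 | 0.95 | 5% | 2.6% | 228 | 82.0% |
| 0.95 | 0.975 | 3% | 1.3% | 234 | 81.0% |

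**Check on ranks.** The formula describes linear adjustment, not Wilcoxon against PO. A simulation with 120 per arm and 4,000 runs per setting therefore compared the Wilcoxon test on changes with a normal-score rank analysis of covariance. The latter stands in for the PO model, so its figures are indicative. The shift was set so that a normal test on changes would have about 80% power.

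| r | Normal data: change vs adjusted | Lognormal data: change vs adjusted |
|---|---|---|
| 0.5 | 0.786 vs 0.892 | 0.779 vs 0.888 |
| 0.7 | 0.773 vs 0.848 | 0.778 vs 0.855 |
| 0.9 | 0.768 vs 0.791 | 0.757 vs 0.793 |

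The pattern agrees with the formula: a material loss at moderate correlation and a small one near 0.9.

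**The case against.** The strongest reply is that nothing here is invalid. The Wilcoxon test on changes is prespecified, keeps its type I error under randomization, and belongs to an exploratory item. Unadjusted Wilcoxon tests are also the SAP's usual exploratory method. That stands: the point is one of efficiency and consistency.

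A reader might infer that n) breaks a protocol rule against change scores. The documents do not go that far. The sentence in 10.0 sits with the primary model, the section defers full methods to the SAP, and the wording about the most powerful analysis is for safety laboratory data, whereas n) is listed as exploratory. The primary outcome is itself a weight change per dose, adjusted for baseline weight. What remains is that the reasoning in 10.0 extends naturally to n), comparable outcomes follow it, and no reason is given for the exception. The clause allowing alternative methods does not supply one, since it applies only when diagnostics suggest violated assumptions.

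A reader might also infer that a renal or electrolyte signal would be hidden, or that creatinine and eGFR could leave two renal answers of equal standing. They would not be of equal standing: eGFR is the designated safety endpoint, is baseline-adjusted, and is run with both MDRD and CKD-EPI. Potassium and glucose have their own analyses of daily values and severity categories under Exploratory o) and Safety c), although those are not baseline-adjusted.

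Finally, the measurements are repeats in the same patient, with treatment lasting at most five days, so high correlations are plausible and the loss may be only a few percent. That also stands, and it is why the range runs to r = 0.95.

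**Conclusion.** The point holds as a minor one. Item n) uses an unadjusted change score where the protocol's reasoning, and the SAP's practice for NT-proBNP, urinary Na/K, congestion score and eGFR, favour the end-of-study value adjusted for baseline. The cost is between about 3% and 54% in equivalent sample size for r from 0.95 down to 0.3, assuming equal variances and a linear relation. Because r is not in the documents, no single figure can be defended. The results also depend on whether raw or log values are differenced.

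The benefit of changing falls mainly on analytes without an analysis of their own, such as BUN, sodium, bicarbonate and hemoglobin. The SAP does not list the panel's components; BUN, sodium, bicarbonate and creatinine appear among its enrollment labs. No bias or type I error problem follows, and no main conclusion of the trial depends on this item.

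**What to change.** Replace the test in Exploratory Analyses n) with PO regression of each end-of-study value on treatment, adjusted for the baseline value of the same analyte, as Safety a) does for eGFR. Enter baseline as a restricted cubic spline with 3 knots, as the primary analysis does for baseline weight. Safety a) itself states no spline, so it is a precedent for the adjustment only. Report changes from baseline as descriptive summaries. If the sponsor prefers to keep the change score, the SAP should say why n) departs from the reasoning in protocol 10.0 and on which scale changes are computed.

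The cost is one SAP sentence. The change score already needs both values, so no data are added, and Main Analysis already provides multiple imputation for missing covariates.
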